6.2.1.3 Assessment of Adverse Events

Each AE will be assessed by the Investigator with regard to the following categories:

- Seriousness
- Intensity
- Causality

6.2.1.3.1 Seriousness

A SAE is defined as any untoward medical occurrence that at any dose:

- Results in death.
- Is life-threatening.
This means that the subject is at risk of death at the time of the event; it does not mean that the event hypothetically might have caused death if it were more severe.
- Requires inpatient hospitalization or prolongation of existing hospitalization.

- Results in persistent or significant disability or incapacity.
- Is a congenital anomaly or birth defect.
- Is an important medical event(s) that may not be immediately life-threatening or result in death or hospitalization but that may jeopardize the subject or require intervention to prevent one of the above outcomes. Examples of such events are intensive treatment in an emergency room or at home for allergic bronchospasm; blood dyscrasias or convulsions that do not result in hospitalization; or development of drug dependency or drug abuse.

Medical and scientific judgment should be exercised in deciding whether a case is serious and whether expedited reporting is appropriate.

6.2.1.3.2 Intensity

The intensity of each AE must be assessed by the Investigator using one of the following categories, and recorded in the eCRF:

- Mild: An AE that does not interfere with usual activities;
- Moderate: An AE that may cause some interference with usual activities;
- Severe: An AE that prevents usual activities and is usually incapacitating.

6.2.1.3.3 Causality

The Investigator will assess the causality/relationship between the study drug and the AE and record that assessment in the eCRF. Causality will be shown as a 'probably related', 'possibly related', 'unlikely related', 'not related' or 'not assessable'.

The most likely cause of an SAE (e.g., disease under treatment, concomitant disease, concomitant medication, other) will be indicated on the eCRF with details of the concomitant disease or medication or other cause.

The causal relationship of the AE to study drug will be described in terms of:

- Probable: the AE:
 - Follows a reasonable temporal sequence from administration of the study drug.
 - Could not be reasonably explained by the subject's clinical state, environmental or toxic factors or other therapies administered to the subject.
 - Disappears or decreases on cessation or reduction in dose of the study drug.
 - Follows a known pattern of response to the study drug.
 - Reappears or worsens upon rechallenge.
- Possible: the AE:
 - Follows a reasonable temporal sequence from administration of the study drug.
 - Could be reasonable explained by the subject's clinical state, environmental or toxic factors or other therapies administered to the subject.
 - Follows a known pattern of response to the study drug.
- Unlikely: the AE
 - Does not follow a reasonable temporal sequence from administration of the study drug.

- Could be reasonably explained by the subject's clinical state, environmental or toxic factors or other therapies administered to the subject.
- Does not follow a known pattern of response to the study drug.
- Does not reappear or worsen upon rechallenge.
- Not related:
 - The AE does not meet the above criteria.
 - There is sufficient information that the etiology of the AE is not related to the study drug.
- Not assessable/unclassifiable:
 - The AE cannot be judged because of insufficient or contradictory information, which cannot be supplemented or verified.

The study conduct relatedness for SAEs will also be assessed and documented.

6.2.1.4 Recording Adverse Events

The period for adverse event reporting will extend from signing of informed consent until 14 days after the last study treatment administration (including placebo during the single-blind placebo washout period). Adverse events occurring after the end of the study should be reported to the Sponsor or Sponsor's designee by the Investigator if the Investigator considers there is a causal relationship with the study drug.

All AEs, regardless of the relationship to study drug, will be recorded in the eCRF. All AE reports should contain a brief description of the event, date and time of onset, date and time of resolution, intensity, treatment required, relationship to study drug, action taken with the study drug, outcome, and whether the event is classified as serious.

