Blinded SUVN-502/placebo treatment and generic formulations of donepezil HCl 10 mg and memantine HCl 10 mg will be dispensed to the subjects for treatment until the next visit.

During the 26-week treatment period, subjects and caregivers will have study visits at Weeks 4, 13, and 26. At each of these visits, subjects will be evaluated for AEs and undergo physical and neurological examination, blood pressure assessment, and ECG. The MMSE, ADAS-Cog, CDR-SB, ADCS-ADL, NPI, C-SDD and C-SSRS scores will be assessed. Urine and blood samples for laboratory evaluations will be collected at Weeks 4 (liver function tests only), 13 and 26. For women of childbearing potential, a pregnancy test will be performed at Week 26. Blood samples for plasma levels of SUVN-502, its metabolite (M1 of SUVN-502), donepezil and memantine will be collected at Weeks 4 and 26.

Subjects who complete the 26-week treatment period, will undergo a 4-week single-blind placebo washout period. At Week 30, subjects will attend a follow-up visit to the study center. During this visit, subjects will be evaluated for AEs and undergo physical and neurological examination, blood pressure assessment, ECG, laboratory evaluations. The C-SDD and C-SSRS scores will be assessed.

Subjects who discontinue treatment prematurely (see Section 4.3) should attend a final visit similar to Week 26 visit and, if subjects agree, the subjects will return 4 weeks later for a follow-up visit similar to Week 30 visit.

During the course of the study, an independent Data and Safety Monitoring Board (DSMB) will be assembled to periodically review and evaluate accumulated study data for subject safety, study conduct and progress. The DSMB will have the responsibility to make recommendations concerning continuation, modification, or termination of the study.

The approximate blood volume to be collected during the study is 135.5 mL, with a maximum of 26 mL per visit.

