4.3 Subject Withdrawal and Replacement

Subjects and caregivers may withdraw from the entire study including follow-up at any time without penalty and for any reason without prejudice to his or her future medical care.

Subjects must be withdrawn from **study drug** under the following circumstances:

- Pregnancy (see Section 6.2.1.7)
- Elevated ALT, AST, or total bilirubin (see Section 6.2.2)
- Suicidal ideation or behavior (see Section 6.2.6.1)

- Treatment with prohibited concomitant medications is required (see Section 5.7.2)
- Treatment with donepezil HCl cannot be maintained at the dose of 10 mg qd or as part of the combination therapy of Namzaric™ (28 mg memantine HCl extended-release / 10 mg donepezil HCl) qd.
- Treatment with memantine HCl cannot be maintained at either 10 mg bid of memantine HCl or 28 mg memantine HCl extended-release qd of Namenda XR® or as part of the combination therapy of Namzaric™ (28 mg memantine HCl extended-release / 10 mg donepezil HCl) qd
- Subject's noncompliance to study treatment (see Section 5.6)
- A medical condition or personal circumstance which, in the opinion of the Investigator and/or Sponsor, places the subject at unnecessary risk through continued participation in the study or does not allow the subject to adhere to the requirements of the protocol

Subjects may be required to withdraw from study drug, according to the Investigator's judgment, for the following reasons:

- AE(s)
- Any reason at the discretion of the Investigator

In all cases, the reason(s) for withdrawal, and the primary reason, must be recorded on the electronic Case Report Form (eCRF). If a subject is prematurely withdrawn from the study drug for any reason, the Investigator must make every effort to perform the evaluations described for the Week 26 visit and a follow-up visit 4 weeks later.

If a subject withdraws consent and still agrees to undergo a final examination, this will be documented on the eCRF and the Investigator's copy of the informed consent form (ICF), which will be countersigned and dated by the subject.

A subject may also be withdrawn from study drug by the Sponsor, Regulatory Authorities, or Independent Ethics Committees (IECs)/Institutional Review Boards (IRBs).

Subjects will also be withdrawn if the entire study is terminated prematurely as described in Section 9.11.

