5 STUDY DRUG

5.1 Identity

5.1.1 Investigational Treatment: SUVN-502 and Matching Placebo

From Day 1 to the end of Week 26, eligible subjects will receive double-blind oral administration of one of following three treatments:

- SUVN-502 50 mg
- SUVN-502 100 mg
- placebo

During the single-blind placebo washout period (Weeks 27 to 30), all subjects will receive placebo.

[REDACTED]

[REDACTED]	[REDACTED]	[REDACTED]	[REDACTED]	[REDACTED]
[REDACTED]	[REDACTED]	[REDACTED]	[REDACTED]	[REDACTED]
[REDACTED]	[REDACTED]	[REDACTED]	[REDACTED]	[REDACTED]
[REDACTED]	[REDACTED]	[REDACTED]	[REDACTED]	[REDACTED]
[REDACTED]	[REDACTED]	[REDACTED]	[REDACTED]	[REDACTED]
[REDACTED]	[REDACTED]	[REDACTED]	[REDACTED]	[REDACTED]
[REDACTED]	[REDACTED]	[REDACTED]	[REDACTED]	[REDACTED]
[REDACTED]	[REDACTED]	[REDACTED]	[REDACTED]	[REDACTED]

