6.2.1.5 Reporting Serious Adverse Events

The Investigator must report any SAEs to the [REDACTED] Clinical Studies Safety Center within 24 hours of becoming aware of the event.

When calling to report an SAE, state that you are reporting an SAE and give the Investigator's name, your name, the telephone number where you can be reached, and the protocol number and title.

The Investigator and the Sponsor (or Sponsor's designee) will review each SAE report and the Sponsor, [REDACTED] will evaluate the seriousness and the causal relationship of the event to study treatment. In addition, the Sponsor (or Sponsor's designee) will evaluate the expectedness according to the reference document (Investigator Brochure or Summary of Product Characteristics). Based on the Investigator and Sponsor's assessment of the event, a decision will be made concerning the need for further action.

All SAEs will be recorded from signing of informed consent until 14 days after the last study treatment administration (including placebo during the single-blind placebo washout period). Serious AEs occurring after the end of the study and coming to the attention of the Investigator must be reported only if they are considered (in the opinion of the Investigator) causally-related to the investigational drug.

- [REDACTED]
1. Telephone the Medical Monitor to inform her that you are faxing a SAE form. If the Medical Monitor is not available or you are calling after business hours (8:30 am to 5:30 pm Eastern time, Monday to Friday), leave a message in her voice mailbox.
 2. Provide the Medical Monitor with the Principal Investigator's name, your name, the telephone number where you can be reached, and the protocol number and title.
 3. Fax the SAE form and any supporting documentation to the Medical Monitor within 24 hours of becoming aware of the event.
 4. After business hours, the Medical Monitor may be reached through [REDACTED] 24-hour answering service [REDACTED]. Give the answering service the protocol number, the study drug name, and the Sponsoring pharmaceutical company.

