7.2.7 Early Termination and Follow-Up Visits

Subjects who discontinue early from the study should, if possible, have an Early Termination visit. This visit should take place as soon as possible after the subject stops taking study drug. The observations and procedures scheduled for Visit 5 (Week 26) should be performed at the Early Termination visit. If the subject agrees, he/she should return for a follow-up visit 4 weeks later. The observations and procedures scheduled for Visit 6 should be performed at the Follow-up visit.

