9.10 Duration of the Study

For an individual subject, the maximum duration of the study for each subject will be up to 34 weeks (including up to 4 weeks for screening, up to 26 weeks of treatment and up to 4 weeks follow-up).

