9.11 Premature Termination of the Study

If the Investigator, the Sponsor, or the Medical Monitor becomes aware of conditions or events that suggest a possible hazard to subjects if the study continues, the study may be terminated after appropriate consultation between the relevant parties. The study may also be terminated early at the Sponsor's discretion in the absence of such a finding.

Conditions that may warrant termination include, but are not limited to:

- The discovery of an unexpected, significant, or unacceptable risk to the subjects enrolled in the study.
- Failure to enroll subjects at an acceptable rate.
- A decision on the part of the Sponsor to suspend or discontinue development of the drug.
- A recommendation from the DSMB to terminate the study.

If the study is terminated prematurely, all withdrawn subjects should attend a final visit with the same procedures as the Week 26 visit.

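### For subjects who stop early and take no washout placebo, the AE/SAE recording window closes before their own 4-week follow-up visit

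*Protocol*

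**What the plan says.** - **Recording window.** Protocol 6.2.1.4 collects AEs from consent "until 14 days after the last study treatment administration (including placebo during the single-blind placebo washout period". For serious events, 6.2.1.5 repeats the rule: "All SAEs will be recorded from signing of informed consent until 14 days after the last study treatment administration", again counting washout placebo.
- **Dosing.** Protocol 5.1.1: "From Day 1 to the end of Week 26, eligible subjects will receive double-blind oral administration". Protocol 3.1 gives the washout to completers: "Subjects who complete the 26-week treatment period, will undergo a 4-week single-blind placebo washout period". The last scheduled visit for completers is Visit 6 (Week 30, Day 210 ±2).
- **Early stoppers.** Protocol 7.2.7 asks for an Early Termination visit as soon as possible after drug is stopped, using the Visit 5 procedures. Then: "If the subject agrees, he/she should return for a follow-up visit 4 weeks later", using the Visit 6 procedures. Protocol 4.3 is firmer: the investigator "must make every effort to perform the evaluations described for the Week 26 visit and a follow-up visit 4 weeks later".
- **What must be documented.** Protocol 6.2.1.2 has all AEs that occur during the study entered in the eCRF.
- **Study termination.** Protocol 9.11: "all withdrawn subjects should attend a final visit with the same procedures as the Week 26 visit". It does not mention the follow-up visit.

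**The concern.** The window is anchored to the last tablet of any kind, and washout placebo counts. Its length therefore depends on whether a subject reached Week 26 and entered the washout, which is a post-randomization outcome. A subject who stops early, possibly because of an adverse event, may have the shortest recording window. It has already closed when that subject attends a visit designed to look for safety problems.

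Two things are at stake. The first is consistency. One site may enter an event that began on day 20 after the last tablet, because it arose during the study and was found at a scheduled AE review. Another may leave it out because 6.2.1.4 stopped at day 14. The second is comparability between arms. SAP 4.8.2 reports counts and percentages of subjects with events, with no stated adjustment for observation time. If more subjects stop early in one arm, ascertainment after drug could differ between arms.

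**Working it through.** **The plan's own total.** Protocol 9.10 states "the maximum duration of the study for each subject will be up to 34 weeks". Its components give 4 (screening) + 26 (treatment) + 4 (follow-up) = 34 weeks, which reproduces.

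**Inputs.** End of double-blind dosing: Day 182 ±3 (5.1.1, Table 3). Visit 6: Day 210 ±2 (7.2.6). Window: last study treatment + 14 days (6.2.1.4, 6.2.1.5). Early stopper's follow-up: Early Termination visit + 28 days (7.2.7). Planning dropout: 20% or less of 179 per arm (8.9).

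**Completers.** Days of recording after the last double-blind tablet = (last placebo day − last double-blind day) + 14.
- Nominal: (210 − 182) + 14 = 42 days, closing on Day 224.
- Last placebo tablet the day before Visit 6: (209 − 182) + 14 = 41 days.
- Over the visit allowances: from (208 − 185) + 14 = 37 to (212 − 179) + 14 = 47 days.

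**Early stoppers who take no washout placebo.** The window is 14 days. Let g be the number of days from the last tablet to the Early Termination visit. The documents give no value for g, so the values below are assumptions. The follow-up visit falls at g + 28, and the interval between window closure and visit is g + 28 − 14 = g + 14.

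| g (assumed) | window closes | follow-up visit | days outside the window |
|---|---|---|---|
| 0 | day 14 | day 28 | 14 |
| 7 | day 14 | day 35 | 21 |
| 14 | day 14 | day 42 | 28 |

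The nominal minimum is 14 days. If the general ±2-day allowance in 7.2 applies to this visit, a visit two days early with g = 0 would make it 12.

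**Early stoppers who do take four weeks of placebo.** 28 + 14 = 42 days, the same as completers. The text does not settle who these subjects are:
- 3.1 gives the washout to those who complete 26 weeks, and 7.2.7 mentions only a return visit. The rationale in Appendix 11 (Change 5) says early terminators are not expected to take washout medication.
- 5.1.1 gives placebo to all subjects in the washout. Table 3 marks dispensation in the column shared by Week 26 and early withdrawal. 7.2.5 lists dispensation among the Visit 5 procedures that 7.2.7 carries over. SAP 4.3.1 has a disposition row for early withdrawals who took placebo.

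**Subjects exposed.** 0.20 × 179 = 35.8, about 36 per arm; 0.20 × 537 = 107.4, about 107 in all.

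**The rules side by side.** The early stopper's follow-up visit includes AE review, laboratory tests and C-SSRS (7.2.6 through 7.2.7). Under 6.2.2 a significantly worsened laboratory value is recorded as an AE. Under 6.2.6.1 suicidal ideation or behavior is reported as an AE. Under 6.2.1.2 all AEs during the study are documented. Under 6.2.1.4 and 6.2.1.5 the recording period has ended. These cannot all be followed for an event that begins on days 15 to 28.

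**The case against.** The strongest answer is that such events would be captured anyway. Protocol 6.2.1.2 requires it, 6.2.1.5 has any SAE reported within 24 hours of the site becoming aware, and the follow-up visit asks about AEs. SAP 4.2.2 summarizes that visit with Week 30, and SAP 4.8.2 sets no end date for treatment-emergent events. This stands to the extent that loss of events is not demonstrated. It does not remove the contradiction, because a site that applies the 14-day limit is also following the protocol.

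A reader might infer more than the documents support:
- *That SAEs on days 15 to 28 are reportable only if judged causally related.* That filter applies after the end of the study. Protocol 5.6 and 8.1.1 treat subjects who have stopped drug but await follow-up as still taking part, so it is not clear that the filter reaches them.
- *That late events are under-counted in the SUVN-502 arms.* The 18 versus 7 discontinuations for adverse events quoted in the Introduction come from a trial of another compound in the class. The excess was mainly asymptomatic, transient transaminase rises. Protocol 6.2.1.6 follows known AEs to resolution or stabilization. With a parent half-life of 12.5 to 13.7 hours (1.1.3), 14 days is 336 / 13.7, more than 24 half-lives. Differential loss is possible, not shown.
- *That the completers' last 14 days contradict 9.10 or need an added contact.* Section 9.10 counts screening, treatment and follow-up, not reporting time. A reporting duty that outlasts the final visit is a design choice, and 6.2.1.1 accepts spontaneous reports.
- *That 9.11 cancels follow-up when the study is stopped.* Section 4.3 lists study termination among withdrawals and asks for the 4-week visit after withdrawal from drug for any reason. Section 9.11 is silent on that visit and does not override it.

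**Conclusion.** The point holds as an internal contradiction in the safety-recording rule. For early stoppers who take no washout placebo, recording closes 14 days after the last tablet, nominally at least 14 days before a scheduled safety visit. Completers have about 42 days (37 to 47 over the visit allowances). Events on days 15 to 28 may be recorded at some sites and not at others.

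The effect on the arm comparison is unknown. About 36 subjects per arm is a ceiling: it takes the full 20% dropout, spread evenly over arms. It includes subjects who die, are lost or decline the visit, and any who do take placebo, for whom the mismatch does not arise. An even spread also implies no difference between arms, so this figure does not measure one.

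The result assumes that study treatment in the window rule means the SUVN-502 or placebo tablet; 5.6 also uses the term for sponsor-supplied donepezil and memantine.

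**What to change.** 1. In 6.2.1.4 and 6.2.1.5, extend AE and SAE recording to the follow-up visit (Week 30, or the 4-week visit after early termination) or to 14 days after the last study treatment, whichever is later. Reconcile this with 6.2.1.2 and 7.2.7.
2. Reconcile the passages on whether early stoppers receive washout placebo: 3.1, 5.1.1, Table 3, 7.2.5, 7.2.7 and SAP 4.3.1. The review takes no position on which is right.
3. In 9.11, cross-refer to the follow-up visit in 4.3.

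This does not equalize the windows. Completers would still have about 42 days, and an early stopper about 28 days or more if the visit is attended. It does ensure that no scheduled safety visit falls outside the recording period. The cost is protocol wording only: the visit and its AE review already exist, so no new contact is needed and 9.10 can stay as it is.

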6.2.1.5 Reporting Serious Adverse Events

The Investigator must report any SAEs to the [REDACTED] Clinical Studies Safety Center within 24 hours of becoming aware of the event.

When calling to report an SAE, state that you are reporting an SAE and give the Investigator's name, your name, the telephone number where you can be reached, and the protocol number and title.

The Investigator and the Sponsor (or Sponsor's designee) will review each SAE report and the Sponsor, [REDACTED] will evaluate the seriousness and the causal relationship of the event to study treatment. In addition, the Sponsor (or Sponsor's designee) will evaluate the expectedness according to the reference document (Investigator Brochure or Summary of Product Characteristics). Based on the Investigator and Sponsor's assessment of the event, a decision will be made concerning the need for further action.

All SAEs will be recorded from signing of informed consent until 14 days after the last study treatment administration (including placebo during the single-blind placebo washout period). Serious AEs occurring after the end of the study and coming to the attention of the Investigator must be reported only if they are considered (in the opinion of the Investigator) causally-related to the investigational drug.

- [REDACTED]
1. Telephone the Medical Monitor to inform her that you are faxing a SAE form. If the Medical Monitor is not available or you are calling after business hours (8:30 am to 5:30 pm Eastern time, Monday to Friday), leave a message in her voice mailbox.
 2. Provide the Medical Monitor with the Principal Investigator's name, your name, the telephone number where you can be reached, and the protocol number and title.
 3. Fax the SAE form and any supporting documentation to the Medical Monitor within 24 hours of becoming aware of the event.
 4. After business hours, the Medical Monitor may be reached through [REDACTED] 24-hour answering service [REDACTED]. Give the answering service the protocol number, the study drug name, and the Sponsoring pharmaceutical company.

